4.4.1 When and How to Withdraw Subjects

Study subjects will be withdrawn from the study if they experience any known or unknown severe adverse event following administration of either Ca-DTPA or Zn-DTPA. Treatment will be discontinued immediately following any severe adverse event.

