8.1 Definitions

Unanticipated Problems Involving Risk to Subjects or Others

Any incident, experience, or outcome that meets all of the following criteria:

- Unexpected in nature, severity, or frequency (i.e. not described in study-related documents such as the IRB-approved protocol or consent form, the investigators brochure, etc)
- Related or possibly related to participation in the research (i.e. possibly related means there is a reasonable possibility that the incident experience, or outcome may have been caused by the procedures involved in the research,

- Serious (as defined below) “**Serious**” is different than “severe” as reported in the CTC criteria that applies a grade to the AE.

Adverse Event

An **adverse event** (AE) is any symptom, sign, illness or experience that develops or worsens in severity during the course of the study. Intercurrent illnesses or injuries should be regarded as adverse events. Abnormal results of diagnostic procedures are considered to be adverse events if the abnormality:

- results in study withdrawal
- is associated with a serious adverse event
- is associated with clinical signs or symptoms
- leads to additional treatment or to further diagnostic tests
- is considered by the investigator to be of clinical significance

Serious Adverse Event

Adverse events are classified as serious or non-serious. A **serious adverse event** is any AE that is:

- fatal
- life-threatening
- requires or prolongs hospital stay
- results in persistent or significant disability or incapacity
- a congenital anomaly or birth defect
- an important medical event

Important medical events are those that may not be immediately life threatening, but are clearly of major clinical significance. They may jeopardize the subject, and may require intervention to prevent one of the other serious outcomes noted above. For example, drug overdose or abuse, a seizure that did not result in in-patient hospitalization or intensive treatment of bronchospasm in an emergency department would typically be considered serious.

All adverse events that do not meet any of the criteria for serious should be regarded as **non-serious adverse events**.

For the purpose of this trial, the following will be considered expected adverse events:

Ca-DTPA—headache, lightheadedness, chest pain, allergic reaction, dermatitis, metallic taste, nausea and diarrhea, and injection site reactions.

Zn-DTPA—headache, lightheadedness, and pelvic pain.

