Possible “flare effect”, resulting in exacerbation of current symptoms.

Adverse Event Reporting Period

The study period during which adverse events must be reported is normally defined as the period from the initiation of any study procedures to the end of the study treatment follow-up. For this study, the study treatment follow-up is defined as 30 days following the last administration of study treatment.

Preexisting Condition

A preexisting condition is one that is present at the start of the study. A preexisting condition should be recorded as an adverse event if the frequency, intensity, or the character of the condition worsens during the study period.

General Physical Examination Findings

At screening, any clinically significant abnormality should be recorded as a preexisting condition. At the end of the study, any new clinically significant findings/abnormalities that meet the definition of an adverse event must also be recorded and documented as an adverse event.

Post-study Adverse Event

All unresolved adverse events should be followed by the investigator until the events are resolved, the subject is lost to follow-up, or the adverse event is otherwise explained. At the last scheduled visit, the investigator should instruct each subject to report any subsequent event(s) that the subject, or the subject's personal physician, believes might reasonably be related to participation in this study. The investigator should notify the study sponsor of any death or adverse event occurring at any time after a subject has discontinued or terminated study participation that may reasonably be related to this study. The sponsor should also be notified if the investigator should become aware of the development of cancer or of a congenital anomaly in a subsequently conceived offspring of a subject that has participated in this study.

Abnormal Laboratory Values

A clinical laboratory abnormality should be documented as an adverse event if any one of the following conditions is met:

- The laboratory abnormality is not otherwise refuted by a repeat test to confirm the abnormality
- The abnormality suggests a disease and/or organ toxicity
- The abnormality is of a degree that requires active management; e.g. change of dose, discontinuation of the drug, more frequent follow-up assessments, further diagnostic investigation, etc.

Hospitalization, Prolonged Hospitalization or Surgery

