8.4 Stopping Rules

The study will be stopped for review if there is greater than 2 of the first 3 patients, or 5 of the first 10 patients experience an unanticipated severe adverse event, or more than one grade IV expected adverse events as defined by CTCAE v.4.0.

Study subjects will be withdrawn from the study if they experience any unknown severe adverse event (grade 3 or 4) following administration of either Ca-DTPA or Zn-DTPA. We will be using the CTCAE v.4.0 scale to measure severity of adverse events.

Any patient who shows a Grade 3 hypocalcemia (<7.0-6.0 mg/dl) post infusion therapy will be discontinued from the study.

The study will be stopped for any study-related death.

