8.5 Medical Monitoring

It is the responsibility of the Principal Investigator to oversee the safety of the study at his/her site. This safety monitoring will include careful assessment and appropriate reporting of adverse events as noted above, as well as the construction and implementation of a site data and safety-monitoring plan (see section 9 Auditing, Monitoring and Inspecting). Medical monitoring will include a regular assessment of the number and type of serious adverse events.

Safety Monitoring will be performed by [name], who is not a study investigator. The CRFs and any relevant source documents will be sent to the medical safety monitor (as above) who will review them after treatment is complete for subject 1, 3, 10 and 20.

The research coordinator will complete the appropriate report form and logs; assist the PI to prepare reports and notify the IRB, FDA, and/or safety monitor of all Unanticipated Problems/SAE's.

The research coordinator and co-principal investigators will confirm that all Adverse effects (AE) are correctly entered into the AE log by the coordinator; be available to answer any questions that the coordinators may have concerning AEs; notify the IRB and FDA of all Unanticipated Problems/SAEs and AEs as appropriate. All assessments of AEs will be made by a licensed medical professional who is an investigator on the research.

Complications will be assessed by the co-PIs, categorized into major and minor categories and recorded on the CRF. CRFs and appropriate source documents will be made available to this individual for bi-monthly (every 2 months) review to ensure completeness of data collection. Any discrepancies will be immediately addressed by the co-PIs. All adverse events will be recorded and then summarized for inclusion in the final manuscript.

Data monitoring will be performed by an individual who is not a study investigator. CRFs and appropriate source documents will be made available to this individual for review to ensure completeness of data collection. Any discrepancies will be immediately addressed by the co-PIs.

- Verify receipt of all documents and supplies needed to conduct study
- Informed consent obtained for each participant
- Source document verification 100%
- CRF completion
- Investigational product accountability
- Check and review of the regulatory binder and all essential documents
- Clinical supply inventory
- SAE reporting
- Protocol amendment and their approval by the IRB

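### Withdrawal after a severe adverse event stops the planned symptom scoring, so pain/QOL scores can be missing for the subjects who did worst; two phrases in 8.4 also need aligning

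*Combined protocol and SAP*

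**What the plan says.** **Who is withdrawn.** Section 4.4.1: "Study subjects will be withdrawn from the study if they experience any known or unknown severe adverse event" after either product. It adds: "Treatment will be discontinued immediately following any severe adverse event". It gives no grade. Section 8.4 covers the same ground in different words: "Study subjects will be withdrawn from the study if they experience any unknown severe adverse event (grade 3 or 4" on the CTCAE v4.0 scale. It separately discontinues any patient with grade 3 hypocalcemia.

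**What counts as expected.** For Ca-DTPA, section 8.1 lists headache and lightheadedness, then "chest pain, allergic reaction, dermatitis, metallic taste, nausea and diarrhea, and injection site reactions". It also lists a possible flare, "resulting in exacerbation of current symptoms".

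**What happens after withdrawal.** Section 4.4.2 repeats the screening laboratory tests and makes one phone call a week after the event. Screening (4.3) also includes pain/QOL assessments, but 4.4.2 carries over only the laboratory part. Section 6.14 and the Time and Events Table provide calls at months 6 and 12. Neither says whether withdrawn subjects are called.

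**What is analysed.** Symptom reduction is the primary endpoint in 3.2 but a secondary objective in section 2. Section 7.2 plans paired pre/post comparisons, defines an all-treated population (at least one dose), and gives no rule for missing scores.

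**When the study pauses.** Section 8.4 stops the study for review if "greater than 2 of the first 3 patients, or 5 of the first 10 patients experience an unanticipated severe adverse event". Section 8.5 sends the data to a non-investigator safety monitor, "who will review them after treatment is complete for subject 1, 3, 10 and 20".

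**The concern.** The event that ends a subject's symptom scoring can be a worsening of the symptom outcome itself. A subject with a severe flare is withdrawn, stays in the all-treated population, and has no planned pain/QOL score afterwards other than possibly the two late calls. Missingness would then depend on the outcome, and the pre/post changes would lean towards subjects who tolerated treatment. The stated aim in 7.2 is to estimate effect size and variation for a future trial, so an optimistic estimate would be carried into that trial's design.

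Two smaller matters sit beside this. Staff who open only the section headed Stopping Rules find a narrower withdrawal trigger than the one in 4.4.1. And the phrase about the first 10 patients can be read as 5 or more, or as more than 5, because the comparison is written only before the 3-patient limit.

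**Working it through.** The plan gives no power, error rate or stopping probability, so there is no figure of its own to reproduce. Event rates and withdrawal numbers below are assumptions, because the documents give none.

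**1. Symptom time-points lost.** The Time and Events Table has five pain/QOL time-points after baseline: visits 4, 8 and 12, and months 6 and 12. Assume that the sheets of the round in which the event occurs are kept.

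| Withdrawn in round | Round visits still to come | Lost if month 6/12 calls are made | Lost if they are not |
|---|---|---|---|
| 1 | V8, V12 | 2 of 5 | 2 + 2 = 4 of 5 |
| 2 | V12 | 1 of 5 | 1 + 2 = 3 of 5 |
| 3 | none | 0 of 5 | 0 + 2 = 2 of 5 |

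**2. Effect on the mean change.** Let all 20 subjects be treated and w of them lack a score. Let m_o be the mean change of those scored, m_w that of those not scored, and D = m_o − m_w, with positive values meaning improvement.

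- Mean of all 20 = [(20 − w) m_o + w m_w] / 20 = m_o − (w/20) D
- Error of the observed mean = m_o − [m_o − (w/20) D] = (w/20) D
- w = 1: 0.05 D; w = 2: 0.10 D; w = 4: 0.20 D

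If the unscored subjects did worse, D is positive and the observed mean is too favourable.

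**3. Withdrawal trigger, side by side.**

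| Severe event | 4.4.1 | 8.4 sentence read alone |
|---|---|---|
| Unknown | withdraw | withdraw |
| Known, such as allergic reaction or flare | withdraw | not required |
| Grade 3 hypocalcemia | withdraw | discontinue, by its own sentence |

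The sections differ only in the second row. Applying both gives the 4.4.1 answer.

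**4. Two readings of the 10-patient limit.** Let p be the chance that a patient has an unanticipated severe event, independent between patients. The first limit, more than 2 of 3, means 3 of 3. With r = 5 or r = 6 as the 10-patient limit:

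P(pause) = p³ + Σ(x = 0 to 2) C(3,x) pˣ (1−p)³⁻ˣ × P(Bin(7,p) ≥ r − x)

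At p = 0.30:

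- r = 5: 0.027 + 0.343 × 0.0288 + 0.441 × 0.1260 + 0.189 × 0.3529 = 0.159
- r = 6: 0.027 + 0.343 × 0.0038 + 0.441 × 0.0288 + 0.189 × 0.1260 = 0.065

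| Assumed p | 5 or more | More than 5 | Gap (points) |
|---|---|---|---|
| 10% | 0.25% | 0.11% | 0.1 |
| 20% | 3.7% | 1.3% | 2.4 |
| 30% | 15.9% | 6.5% | 9.4 |
| 40% | 37.7% | 19.3% | 18.4 |
| 50% | 63.1% | 40.5% | 22.6 |

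These figures leave out the grade IV and death rules.

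**The case against.** Several points on the other side stand.

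- **Re-dosing.** A reader might infer from 8.4 that a subject can be treated again after a severe expected reaction. The documents do not support that. Section 4.4.1 stops treatment after any severe event without exception, and 8.4 does not say that its trigger is the only one.
- **Flares.** A reader might infer that any flare ends participation. Only a severe one does.
- **Symptoms after withdrawal are not ignored.** Section 8.1 records worsening of a preexisting condition as an adverse event and has unresolved events followed. Section 8.2 has events sought at each contact. But an adverse event record is not a scale score, and the pre/post analysis needs the score.
- **Late calls.** They exclude nobody by their wording. If they are made, the loss falls to 2, 1 or 0 time-points. The gap is that 4.4.2 and 6.14 leave this open.
- **Status of symptoms.** Section 2 puts urinary gadolinium first, so the weight of the bias depends on which section defines the primary outcome.
- **Stopping limit.** Section 1.4 reports 485 contaminated workers given 3077 doses, with minor transient effects in 12 and none serious. That is a different population, but it does not point to rates of 30% or more. A reader might infer that the ambiguity leaves the study unwatched. It does not: the monitor reviews data after subjects 3 and 10 under either reading.
- **Grade IV limit.** A reader might want "or more than one grade IV expected adverse events as defined by CTCAE v.4.0" rewritten. More than one means two or more, and with no window stated it applies throughout the study. No change is needed.

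**Conclusion.** The main point holds: 4.4.1 and 4.4.2 together allow symptom scores to go missing because of the symptom outcome. The error in the mean change is (w/20) × D, or 5% to 20% of D for an assumed 1 to 4 unscored subjects. This takes 20 treated subjects with the others fully scored, and D is unknown. It would be going too far to say that the study's conclusion would reverse. The number of withdrawals is not known in advance, and 7.2 makes estimation the goal, so no decision hangs on one p-value.

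The mismatch between 4.4.1 and 8.4 is real but secondary, since the stricter rule governs when both are read. The 10-patient ambiguity is minor: about 0.1 points at an assumed 10% event rate and 2.4 at 20%. It matters only if unanticipated severe events are common. Confidence is high on the wording and lower on the practical impact, which rests on assumed numbers.

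**What to change.** **Section 4.4.2 (main change).** State that withdrawal for an adverse event applies to treatment only. Continue the scheduled pain/QOL questionnaires and the month 6 and 12 calls for withdrawn subjects who agree, and include those scores in the all-treated analysis. The cost is a few phone questionnaires on the existing schedule, at most four time-points per withdrawn subject if the triggering round's sheets are kept.

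**Section 8.4, trigger.** Use the 4.4.1 scope: any known or unknown severe event, grade 3 or higher. If the investigators want a condition that the event be new or worse than at baseline, which is reasonable in a symptomatic population, present it as a change to both sections, because neither contains it now. The cost is wording only.

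**Section 8.4, study limit.** Write 5 or more of the first 10. Compared with the other reading, a pause becomes about 0.1, 2.4 or 9.4 points more likely at assumed rates of 10%, 20% or 30%. The pause is for review, so the cost is a possible delay.

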4.4.2 Data Collection and Follow-up for Withdrawn Subjects

The same labs done at screening will be collected, and a follow up phone call will be made one week after the event.

5 Study Drug

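### Sections 4.4.1 and 8.4 give the patient withdrawal rule different scope, and 4.4.2 leaves symptom follow-up after withdrawal unstated

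*Combined protocol and SAP*

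**What the plan says.** Section 4.4.1 says that subjects will be "withdrawn from the study if they experience any known or unknown severe adverse event following administration of either Ca-DTPA or Zn-DTPA". It adds, with no qualifier: "Treatment will be discontinued immediately following any severe adverse event". It gives no grade.

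Section 8.4 states the patient-level rule again: "Study subjects will be withdrawn from the study if they experience any unknown severe adverse event (grade 3 or 4". This is the only place that ties severe to CTCAE v4.0 grades, and it leaves out *known* events. The other actions in 8.4 are:

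- a study-level stop for review on counts of unanticipated severe events among the first 3 and first 10 patients;
- a study-level stop for review on "more than one grade IV expected adverse events as defined by CTCAE v.4.0";
- a patient-level rule for one named event, which begins "Any patient who shows a Grade 3 hypocalcemia";
- a study stop for a study-related death.

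The expected events are in 8.1, under the sentence "For the purpose of this trial, the following will be considered expected adverse events". The Ca-DTPA and Zn-DTPA lists are followed directly by a possible flare effect, "resulting in exacerbation of current symptoms". Hypocalcemia is on neither list.

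For data after withdrawal, 4.4.2 says only: "The same labs done at screening will be collected, and a follow up phone call will be made one week after the event". Section 7.2 plans paired comparisons of baseline with each treatment in the all-treated population and says nothing about missing later rounds.

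**The concern.** The two sections state one rule, in nearly the same words, for different sets of events. *Known* and *unknown* are not defined, and no text says which section governs. Section 8.1 uses expected and unexpected instead. Reading *unknown* as not expected is an inference, but it fits 8.4, whose first sentence already treats unanticipated severe events and grade IV expected events separately. On that reading, a member of staff who consults only the stopping rules finds no instruction for a patient with a severe event of a listed kind.

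Two features make this more than editorial. The expected events overlap with the disease: headache is both an entry symptom (4.1) and an expected event, chest wall pain and chest pain are close, and flare is by definition a worsening of existing symptoms. And Zn-DTPA follows Ca-DTPA the next day, so a re-dosing decision may be needed within about a day. The safety monitor's scheduled reviews in 8.5 come after treatment is complete for subjects 1, 3, 10 and 20, too late to catch a re-dose.

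The second issue does not depend on the first. A patient withdrawn for a severe flare has worsened on what 3.2 names as the primary endpoint. If symptom scores then stop, the later-round comparisons are made without some of the patients who did badly.

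**Working it through.** There is no plan figure to reproduce. The check sets the two sections side by side and then counts from the schedule.

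**Step 1. Action for each type of event, reading *unknown* as not expected (an assumption).**

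| Event | 8.4 alone, patient level | 8.4 alone, study level | 4.4.1 |
|---|---|---|---|
| Unexpected, grade 3 or 4 | Withdraw | Counts towards the review stop | Withdraw, stop treatment |
| Expected (incl. flare), grade 3 | None stated | None stated | Withdraw, stop treatment |
| Expected (incl. flare), grade 4, a single event | None stated | None (needs more than one) | Withdraw, stop treatment |
| Grade 3 hypocalcemia (not listed in 8.1) | Discontinue | None specific to hypocalcemia | Withdraw, stop treatment |

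The 4.4.1 column takes severe to mean grade 3 or 4, since 8.4 names CTCAE v4.0 as the severity scale. The sections diverge in the second and third rows. The hypocalcemia rule does not fill the gap, because hypocalcemia is not a listed expected event.

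**Step 2. Doses at issue.** Inputs: 3 rounds, each with one Ca-DTPA and one Zn-DTPA infusion (Study Summary; 5.2).

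- Planned infusions: 3 × 2 = 6.
- Infusions left after an event following infusion k: 6 − k, which is 5, 4, 3, 2, 1 for k = 1 to 5.

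Section 4.4.1 stops all of these. Section 8.4 alone names no stop for the second and third rows.

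**Step 3. Symptom data at issue.** Inputs: 3 round comparisons with baseline (7.2), 20 planned subjects (7.1), a day-7 contact in each round, and calls at months 6 and 12 (6.14; Time and Events Table).

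- Later rounds left after withdrawal in round r: 3 − r, which is 2, 1, 0 for r = 1, 2, 3.
- Share of planned pairs per patient: 1/20 = 5%.
- Pain/QOL contacts left: (3 − r) + 2 = 4, 3, 2 for r = 1, 2, 3.

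The last count takes the round of withdrawal as covered by its own day 1–6 sheets and by the one-week call already in 4.4.2.

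**Step 4. What cannot be computed.** The documents give no rate for severe expected events or flares. Neither the number withdrawn nor the size of any shift in the symptom results can be estimated.

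**The case against.** The strongest reply is that the two rules are compatible. Section 4.4.1 is the section devoted to withdrawal, its second sentence covers any severe event, and 8.4 restates part of it without saying that anyone else continues. A team that follows both will stop treatment. This stands, and it rules out the stronger reading that the protocol lets patients be re-dosed after a severe expected event.

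Other safeguards also exist. Section 4.4 allows removal for safety concerns, and section 6 closes by allowing evaluation and possible discontinuation between treatments. The trial has one center, and an investigator gives the injections. These lower the chance of harm, but they are discretionary and do not settle which wording applies.

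On the data side, a reader might infer that all symptom data stop at withdrawal. The documents do not support that. Section 4.4.2 is silent, not prohibitive; a flare can be recorded on the day 1–6 sheets of its own round; and the month 6 and 12 calls do not exclude withdrawn patients. Nor do the documents support calling the symptom results biased. A tilt towards improvement assumes that withdrawn patients' later scores would be worse than those of patients who remain, and a short-lived flare might not have that effect.

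It is also fair to say that aligning 8.4 does nothing for missing symptom data. The two issues need separate fixes. Finally, this is an uncontrolled feasibility study aimed at estimation. That limits the consequences, but its purposes include the safety profile and endpoints for a future trial, and both issues bear on these.

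**Conclusion.** The point holds as an inconsistency in a safety rule, not as a missing rule. Read together, the sections stop treatment after any severe event. Read alone, and if *unknown* means not expected, 8.4 gives no patient-level action for a grade 3 or a single grade 4 expected event, and from 1 to 5 infusions may still be planned when the event occurs. The harm needs a reader who uses 8.4 without 4.4.1, takes that meaning, and re-doses. That is possible but not shown to be likely.

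The separate 4.4.2 gap also holds. A patient withdrawn in round 1 or 2 may be missing from 2 or 1 of the 3 round comparisons, at 5% of planned pairs each. This could tilt those comparisons towards improvement by an amount that cannot be estimated. No figure stated in the plan changes. Both should be corrected because the changes are small and the first only carries into 8.4 what 4.4.1 already requires.

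**What to change.** In 8.4, replace the patient-level wording with: *any severe adverse event (CTCAE v4.0 grade 3 or 4), expected or unexpected, including the events listed in 8.1 and the flare effect*. Use the same wording in 4.4.1. This drops the undefined terms and puts the grades in both places. No patient loses a dose beyond what 4.4.1 already requires.

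In 4.4.2, state that patients withdrawn from treatment who agree to further contact give one pain/QOL assessment by phone on the calendar dates when their remaining day-7 visits would have fallen, counted from the first infusion, and at months 6 and 12. Fixed dates are needed because a withdrawn patient has no later infusion to count from. Daily day 1–6 sheets are not required after withdrawal. Patients who decline contact are simply recorded as such. Report the number withdrawn for flare beside the symptom results.

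The cost is one phrase used in two sections, one addition to 4.4.2, one reported count, and at most 4 phone contacts per withdrawn patient, 2 of them already in the schedule.
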